### 2.3.6 Baseline Testing: Population 1 (Adults)

Once candidacy has been determined, auditory function will be evaluated in order to establish a baseline level on those that meet criteria. The tests will be administered using the same bilateral hearing aids used to determine candidacy. The following battery of measures will be administered:

#### 2.3.6.1 Speech Perception Testing

1. Consonant-Nucleus-Consonant monosyllabic words (CNC, Tillman & Carhart, 1966) in quiet. Two lists of CNC words will be administered in each test condition. Testing will be attempted in the ear to be implanted and bilaterally at 60 dBA.

2. The AzBio sentence (Spahr & Dorman, 2005) lists were created from a corpus of 1000 sentences recorded by 4 untrained speakers, 2 male and 2 female. The original recordings from each speaker were normalized to be approximately equal in level (dB RMS). The materials were processed using a 5-channel cochlear implant simulation and presented to 15 normal-hearing listeners to determine the average level of intelligibility for each sentence. The results allowed for the creation of 33 lists of 20 sentences. Each list includes 5 sentences from each of the 4 speakers and the average level of intelligibility of each list is 85% +/- 1%. Two lists of the AzBio sentences will be presented at a target presentation level of 60 dBA with a +5 dB signal-to-noise ratio or SNR (i.e., the competitor will be set to 55 dBA). For baseline testing, the target and competitor will be presented from the same speaker at 0° azimuth using appropriately fit hearing aids unilaterally for the ear to be implanted and bilaterally.

3. A Speech Reception Threshold (SRT) (Turner et al., 2004) is a 12-item forced-choice test in which the patient listens for one of 12 target spondees spoken by a female (birthday, drawbridge, eardrum, iceberg, mousetrap, northwest, padlock, playground, sidewalk, stairway, toothbrush, and woodwork). The target stimulus is delivered under the control of custom software in the presence of either speech (i.e., two competing talkers, one male, and one female) or broad band noise. The speech consists of each competing talker repeating the same sentence (each talker a different sentence) for each stimulus presentation. The level of the competing signal is adaptively varied depending on the subject's response. That is, the level increases (i.e., producing a more aversive signal-to-noise ratio) when a correct response is made and decreased (i.e., producing a less aversive signal-to-noise ratio) when an incorrect response is made. For this study the target stimulus will be presented from a loudspeaker located at 0° azimuth at 60 dBA. The competing signal will be directed towards the right ear (90° azimuth) or towards the left ear (270° azimuth). The initial presentation level of the competing signal is more arbitrarily set, but generally at, or close to, the same level as the target level. The level of the competitor is then varied adaptively up or down depending on the subject's response. The level initially varies in 8 dB steps, progressing to 4 dB and finally 2 dB steps. A threshold is established once 14 reversals are obtained. Threshold is calculated as the average of the levels at which each of the last 10 reversals occurred. The competing signal is directed towards a different channel on the audiometer such that the competitor could be presented from either the same location as the target speech signal or from a loudspeaker located elsewhere. A lower signal-to-noise ratio (SNR) to achieve 50% recognition indicated improvement. In other words, equivalent speech understanding is maintained at a more aversive SNR. Testing will be attempted using appropriately fit hearing aids contralaterally to the ear to be implanted and bilaterally.

Care must be taken to plug the contralateral ear, or provide contralateral masking, when a hearing aid is removed for a test condition (e.g. unilateral testing).

#### 2.3.6.2 Localization Testing

1. A multiple loudspeaker Everyday Sounds Localization Test (Dunn, Tyler, & Witt, 2005) using 16 different sound items will be administered. Localization performance will be determined by calculating the Average Root Mean Square (RMS)-error in degrees. Testing will be attempted bilaterally using appropriately fit hearing aids at 60 dBA.

#### 2.3.6.3 Music Perception

1. Real World Melody Recognition (CMR-R; Gfeller, Olszewski, Turner, Gantz, Oleson, 2006). This test examines the influence of speech and pitch perception in the recognition of excerpts from “real-world” melodies. Testing will be attempted using appropriately fit hearing aids in the ear to be implanted at 70 dBA.

2. Modified Melodies Test: Nudge 2 (MMT; Swanson, Dawson, McDermott, 2009). This test assesses the ability of participants to detect pitch errors in two familiar melodies: Old MacDonald and Twinkle Twinkle when specific notes are modified/nudged by 2 semitones. Testing will be attempted using appropriately fit hearing aids in the ear to be implanted at 70 dBA.

3. Complex-Tone Pitch Discrimination (CTPD, Gfeller, Turner, Woodworth, Mehr, Fearn, Witt, Stordahl, 2002). This test assesses the participants’ ability to discriminate direction of pitch change as a function of interval size (fundamental frequency range, 131-1048 Hz). This adaptive test results in a threshold (across all frequencies) at which the participant is able to achieve 75% accuracy. This is a brief test (5-10 minutes) that can be repeatedly administered in multiple conditions accurately. Testing will be attempted using appropriately fit hearing aids in the ear to be implanted at 70 dBA.

4. Iowa Test Appraisal of Sound Quality (ITASQ, Gfeller, Witt, Woodworth, Mehr, and Knutson, 2002). This test evaluates participants’ appraisal of timbre and sound quality of music instruments and real-world music with and without lyrics. Using 4 bipolar adjective scales, participants describe the sound quality of the each excerpt and also rank their preference for the sound. Testing will be attempted using appropriately fit hearing aids in the best aided condition at 70 dBA.

#### 2.3.7 Baseline Testing: Population 2 (Children and Adolescents)

##### 2.3.7.1 Speech Perception Testing

1. Phonetically Balanced-Kindergarten (PB-K, Haskins, 1949) word test in quiet. The PB-K test has multiple 50 word lists. The test will be scored as total number of words correct as well as phonemically. Testing will be attempted using appropriately fit hearing aids in the ear to be implanted and bilaterally at 60 dBA. This will be administered to children between the ages of 5-6 years.

2. Consonant-Nucleus-Consonant monosyllabic words (CNC, Tillman & Carhart, 1966) in quiet. Two lists of CNC words will be administered in each test condition. Testing will be attempted in the ear to be implanted and bilaterally at 60 dBA. This will be administered to children between the ages of 7-15 years.

3. Computer-assisted Speech Perception Assessment Test (CASPA, Boothroyd, 2004; Mackersie, Boothroyd, & Minniear, 2001) in noise using 20 sets of 10 CVC words. Testing will be administered to children and adolescents between the ages of 7-15 years at 65 dBA speech level with a +10 signal to noise ratio. Testing will be attempted in the ear to be

implanted and bilaterally. Results will be scored in terms of percent correct whole word and percent correct phonemes.

Care must be taken to plug the contralateral or ipsilateral ear, or provide contralateral masking when testing individual ears.

#### 2.3.7.2 Localization Testing

1. A multiple loudspeaker *Everyday Sounds Localization Test* (Dunn, Tyler, & Witt, 2005) using 16 different sound items will be administered. Localization performance will be determined by calculating the Average Root Mean Square (RMS)-error in degrees. Testing will be attempted bilaterally using appropriately fit hearing aids at 60 dBA to children between the ages of 7-15 years.

#### 2.3.7.3 Speech Language Testing

1. *Peabody Picture Vocabulary Development Scale* (PPVT, Dunn & Dunn, 1997). The PPVT is a standardized, norm-referenced measure of receptive vocabulary skills. The test is a multiple-choice measure consisting of sets of four black and white line drawings. The examiner names one of the pictures and the test recipient is expected to indicate which picture has been labeled, either verbally or through pointing. It is appropriate for children and adults from 2 years, 6 months to 90 years, 11 months of age. Testing will be attempted bilaterally.

2. *Goldman Fristo Test of Articulation* (GFTA, Goldman & Fristoe, 2000). The GFTA-2 is a standardized, norm-based articulation measure that samples spontaneous sound production. Children are asked to respond to picture plates and verbal cues from the examiner with single words that test consonant accuracy in initial, medial, and final positions. This measure has norms based on the performance of normal-hearing children from age 2 years to 21 years. Testing will be attempted bilaterally.

3. *Woodcock Reading Mastery Test* (WRMT-R/NU, Woodcock, 1998). These tests are standardized from kindergarten through high school. The Word Identification and Word Attack subtests from the WRMT-R will be used to assess children's *word recognition* abilities. These subtests measure accuracy of sight word recognition and phonetic decoding of pronounceable non-words. *Reading comprehension* abilities will be assessed by the Passage Comprehension subtest of the WRMT-R. The WRMT-R uses a cloze procedure in which the participants are asked to read a short passage and orally provide a missing word. It is appropriate for children and adults from 5 years, 0 months to 20 years, 0 months of age. Testing will be attempted bilaterally.

4. *Comprehensive Assessment of Spoken Language* (CASL, Carrow- Woolfolk, 1999) Carrow-Woolfolk, 1999) is a standardized, norm-referenced measure of oral language skills. It is appropriate for children ages 3 to 21 years of age. The test is composed of core battery of measures which represents different aspects of language categories (semantics, syntax, and pragmatics). Testing will be attempted bilaterally.

#### 2.3.7.4 Music Perception

1. *Complex-Tone Pitch Discrimination* (CTPD, Gfeller, Turner, Woodworth, Mehr, Fearn, Witt, Stordahl, 2002) assesses the participants' ability to discriminate direction of pitch change as a function of interval size (fundamental frequency range, 131-1048 Hz). This adaptive test results in a threshold (across all frequencies) at which the participant is able to achieve 75% accuracy. This is a brief test (5-10 minutes) that can be repeatedly administered in multiple conditions accurately. It is administered in the best aided condition in the ear to be implanted at 70 dBA.

2. *Melody Recognition by Information Level* (MRIL, Olszewski, Gfeller, Froman, Stordahl, Tomblin, 2005) assesses the participants' ability to recognize and identify simple melodies in closed set provided in 4 different formats: sung with video, sung without video, melody with rhythm, and isochronous (melody without rhythm) in random order. Previous research with children and adults who use CIs has shown that while adults with traditional long-electrode cochlear implants are able to perform successfully in three of the four formats (performing poorly on the isochronous condition), adults with short-electrode cochlear implants are able to perform successfully on all formats. Conversely, children with long-electrode devices are only able to perform well on those that include lyrics and perform at or below chance on the other two conditions. It is administered in the best aided condition in the ear to be implanted at 70 dBA.

#### 2.3.7.5 Calibration

Speech perception, music perception, and localization tests will be calibrated using a calibration tone (or calibration sound file). A sound-level meter will be used to measure the dBA level of the calibration tone at a distance of 1 meter from the loudspeaker. The loudness will be adjusted through the audiometer or receiver to achieve the desired loudness level for the specific test.

#### 2.3.8 Surgical Procedure

The surgical procedure for the Nucleus Hybrid L24 and Hybrid S12 cochlear implant requires care to prevent inner ear damage. These procedures are the same as described in IDE No. G070191 and G070016. See ATTACHMENT 1 for a letter from the Sponsor of IDE No. G070191 and G070016 authorizing the FDA to review the information in IDE No. G070191 and G070016 for purposes of the current IDE application.

The most important tenets are given below.

1. A complete mastoidectomy with preservation of the cortex in the area of the tegmen mastoideum performed. Completion of exposure, bony work, and soft tissue work before completing the cochleostomy. This includes drilling a seat for the electronic package, harvesting and constructing a temporal fascia washer. The facial recess or posterior tympanotomy must be opened to allow complete visualization of the round window. The overhanging niche of the round window must be removed using a diamond burr completely exposing the entire round window membrane. These steps minimize the open cochlea's exposure to blood and bone dust. A suture is placed through the boney over hang at the tegmen mastoideum to secure the electrode lead prior to placing the electrode in the scala tympani. This suture stabilizes the springy lead of the implant and prevents translational movement in the scala tympani as the electrode is advanced.

2. Minimally traumatic cochleostomy. A strategy similar to that used to perform a 'drill-out' stapedectomy. This includes making sure bleeding is controlled, bone is slowly removed over the area of the cochleostomy leaving the endosteum of the inner ear intact, and not using suction in the area of an open inner ear. The cochleostomy must be placed approximately 1 mm anterior and inferior to the floor attachment of the round window membrane. The promontory of the cochlea in this portion can be more than 1 mm thick. It is suggested that the promontory be saucerized in this region with a 1-mm diamond burr. Placement of the cochleostomy in the anterior-inferior position to the round window membrane avoids damage to the scala media and spiral ligament. The burr should not enter the scala tympani. The endosteum is opened with a 0.2-mm footplate hook. The smallest cochleostomy needed to insert the implant is made (0.7–0.8 mm). No suctioning of the perilymph is permitted.

3. Minimally traumatic insertion. Short lapse of time between opening the cochlea and insertion is emphasized. The electrode is stabilized with a suture at the lateral tegmen

mastoid cortex prior to insertion into the cochlea. Actual insertion of the electrode is slow (30–45 s) to minimize intracochlear trauma. The fascia washer seals the cochleostomy. No further packing in the scala tympani is allowed.

## **2.4 Postoperative Procedures**

### **2.4.1 Device Activation**

One day prior to activation, subjects without a contraindication to glucocorticoid therapy will be started on prednisone 1mg/kg for 1 week. Subjects will be asked to undergo weekly audiometric testing for one month to monitor acoustic hearing. If drops in threshold of 15 dB HL or more at 125, 250, or 500 are observed, additional prednisone 1mg/kg will be prescribed for 14 days with a gradual taper off over the following week.

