#### 2.4.3 Audiologic Follow-up

##### Audiological Testing:

Unaided audiometric thresholds will be obtained for each ear, with insert earphones whenever possible, using the standard audiometric technique for pure-tone air-conduction testing. During the first month after activation of the Hybrid implant, subjects will be seen on a weekly basis to measure residual acoustic hearing. If more than a 10 dB downward threshold shift is identified, oral prednisone 1mg/kg once a day for 7 days will be prescribed. If hearing is regained or continues to fluctuate, the treating physician and the patient would discuss another trial with the prednisone. If after use of the prednisone there is no change in hearing, the prednisone will be stopped. Additional audiologic follow-up will occur at intervals of 3, 6, 12, and 24 months in adults and at intervals of 4, 8, 12, 18, 24 months, and annually thereafter for three years in children and adolescents.

Unaided (and aided if necessary) testing, for both ears, will include the following:

- Unaided Air Conduction thresholds at 125, 250, 500, 750, 1000, 1500, 2000, 3000, 4000, 6000, and 8000 Hz;
- Bone conduction thresholds at 125, 250, 500, 750, 1000, 1500, 2000, and 4000 Hz;

- Aided Air Conduction thresholds at 125, 250, 500, 750, 1000, 1500, 2000, 3000, and 4000 Hz;

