#### 2.5 Adverse Effects

Adverse effects are any undesirable clinical or medical occurrence associated with use of the device or participation in the study. Any adverse effects are to be reported to the FDA and our IRB via the "Adverse Effects Form". The Primary Investigator will be required to verify that there are or there are no adverse effects to report.

Adverse effects will be reported if observed, even if acknowledged as risk factors in the consent. Adverse effects include:

1. Sudden changes in residual low-frequency hearing. Specifically, a PTA at 125, 250, 500 HZ that is  $\geq 30$  dB HL.
2. Total loss of residual hearing
3. Vertigo, dizziness, or balance problems that did not exist preoperatively or worsened postoperatively
4. Facial nerve problems
5. Meningitis
6. Perilymphatic fistulae
7. Tinnitus that did not exist preoperatively or worsened postoperatively
8. Implant Migration/Extrusion
9. Skin flap problems
10. Device-related/programming problems
11. Infection requiring explantation
12. Device failure requiring explantation

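### Sections 2.4.1 and 2.4.3 of the protocol prescribe different prednisone courses for the same low-frequency hearing drop in the month after activation

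*Protocol*

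**What the plan says.** Protocol section 2.4.1 (Device Activation) starts a preventive course one day before activation: "subjects without a contraindication to glucocorticoid therapy will be started on prednisone 1mg/kg for 1 week". It then sets up monitoring: "Subjects will be asked to undergo weekly audiometric testing for one month to monitor acoustic hearing". The rescue rule follows: "If drops in threshold of 15 dB HL or more at 125, 250, or 500 are observed", then "additional prednisone 1mg/kg will be prescribed for 14 days with a gradual taper off over the following week".

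Protocol section 2.4.3 (Audiologic Follow-up, under Audiological Testing) sets up the same monitoring: "During the first month after activation of the Hybrid implant, subjects will be seen on a weekly basis to measure residual acoustic hearing". Its rescue rule is: "If more than a 10 dB downward threshold shift is identified, oral prednisone 1mg/kg once a day for 7 days will be prescribed". On what comes next it says: "If hearing is regained or continues to fluctuate, the treating physician and the patient would discuss another trial with the prednisone". It adds that prednisone is stopped if hearing has not changed after the course.

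Neither section refers to the other. Neither is limited to adults or to children.

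**The concern.** Both rules act on the weekly audiograms of the same month, in the same subjects, and both are worded as instructions. Where a low-frequency drop meets both triggers, the protocol orders two different durations of a systemic steroid at 1 mg/kg, one with a taper and one without, and does not say which applies.

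At stake are subject safety and uniform conduct. Two subjects with identical audiograms, including children as young as five, could be treated for different lengths of time simply because staff looked in different sections. The collision falls at 125, 250 and 500 Hz, the frequencies whose average defines the first adverse effect listed in section 2.5 ("Specifically, a PTA at 125, 250, 500 HZ that is" 30 dB HL or more). The rules therefore diverge over the low-frequency hearing that the study sets out to preserve and monitors for safety. The clash does not alter that adverse-effect definition or how it is reported.

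A lesser point is that the limit to subjects without a glucocorticoid contraindication is written only for the activation course. It is not repeated for either rescue course.

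**Working it through.** The plan states no figure to reproduce. The check sets the two rules side by side and then counts days.

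| | Section 2.4.1 | Section 2.4.3 |
|---|---|---|
| Window | Weekly for one month, around activation | Weekly in the first month after activation |
| Trigger | Drop ≥ 15 dB at 125, 250 or 500 Hz | Downward shift > 10 dB, no frequency named |
| Full dose | 1 mg/kg, 14 days | 1 mg/kg once a day, 7 days |
| Taper | Over the following week | None stated |
| Further drug | Part of the fixed course | Discussed if hearing is regained or fluctuates; stopped if unchanged |
| Status | Will be prescribed | Will be prescribed |

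**Overlap of triggers.** A drop of at least 15 dB is always more than 10 dB, and section 2.4.3 excludes no frequency. So every event that triggers 2.4.1 also triggers 2.4.3. The reverse is not true: a shift above 10 dB but below 15 dB, or one confined to other frequencies, falls under 2.4.3 alone. That is a difference of scope and not a contradiction.

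**Can both be followed?** They agree for the first 7 days and then part.
- Hearing unchanged after 7 days: 2.4.3 stops the drug; 2.4.1 requires 14 − 7 = 7 more full-dose days and then a taper.
- Hearing regained or fluctuating: 2.4.3 makes more drug a matter for discussion; 2.4.1 makes it automatic.

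**Size of the difference for one such event.**
- Full-dose days: 14 against 7; 14/7 = 2.0.
- Total days with the taper week: 14 + 7 = 21 against 7.
- Full-dose amount, assuming once-daily dosing in 2.4.1 (only 2.4.3 states it): 14 × 1 = 14 mg/kg plus taper, against 7 × 1 = 7 mg/kg.
- With one repeat agreed under 2.4.3: 7 + 7 = 14 full-dose days, equal to 2.4.1, so only the taper differs.
- Cumulative, adding the 7-day activation course given under either rule: 7 + 14 = 21 against 7 + 7 = 14 full-dose days (21/14 = 1.5), and 28 against 14 days in all.

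**Who is covered.** Section 1 plans 15 adults and 30 children and adolescents: 15 + 30 = 45, of whom 30/45 = 67% are aged 5 to 15. No rate of such drops is given, so the number affected could be anywhere from 0 to 45.

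**The case against.** The best defence is that the rules are tiers. Section 2.4.1 is the narrower rule (a larger drop at three named frequencies) with the longer course; section 2.4.3 is the broader rule with the shorter one. Letting the specific rule override the general one is ordinary practice, and both start the same drug at the same dose. This is a plausible guess at the intention, but the text does not say it, and the instruction in 2.4.3 to stop when hearing is unchanged does not fit a fixed 14 days. If thresholds are taken in 5 dB steps (an assumption; the protocol gives no step size), more than 10 dB and 15 dB or more are the same shift, so a tier could rest on frequency only. The word additional in 2.4.1 does not help either: it refers back to the activation course.

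Other objections stand in part:
- The twofold ratio describes the rescue course alone. Counting the activation course, cumulative full-dose exposure differs by a factor of 1.5.
- The contraindication limit can reasonably be read as carrying forward to the additional course in 2.4.1. Only 2.4.3 is wholly unqualified, so this is a secondary drafting point.
- The documents do not show harm from either duration, and this is a small feasibility study with a treating physician involved.

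These points limit the size of the problem. They do not remove the conflict.

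**Conclusion.** The concern holds. For a drop of 15 dB or more at 125, 250 or 500 Hz in the first month after activation, the protocol orders two courses that cannot both be followed: 14 full-dose days plus a one-week taper, or 7 full-dose days with no taper stated. Either duration may be clinically defensible; the fault is that both are required for one event and neither is given precedence.

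The conclusion assumes that both rules measure the drop from the same reference audiogram, since neither section names one. The day counts come directly from the text. They shrink to a difference in taper only if a repeat course is agreed under 2.4.3. How many subjects this would touch cannot be estimated from the protocol. It should be fixed because it concerns systemic steroid dosing in a study where two thirds of planned subjects are children or adolescents. No bias in the efficacy comparison is claimed.

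**What to change.** Replace the two rescue rules with a single one, stated once and cross-referenced from the other section. Either of these would do, as the clinical team decides:

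- **Tiered rule:** a drop of 15 dB or more at 125, 250 or 500 Hz receives 14 days plus the one-week taper; any other downward shift of more than 10 dB receives 7 days.
- **Single course:** one stated duration and taper for all qualifying shifts.

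In either case, say whether the stopping rule for unchanged hearing applies to the 14-day course, say whether the 7-day course is tapered, and apply the glucocorticoid contraindication limit to every course.

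The cost is a short protocol amendment to the prednisone sentences in sections 2.4.1 and 2.4.3. It adds no visits, tests or data items.
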